9.1.4. Exit Contact (Day 28±3)

The Exit Contact will be conducted through Telehealth, online, by telephone, or by text messaging.

Exit Contact evaluations are as follows:

- Collect mid-nasal swab for PCR
- Review AEs
- Complete Exit Contact Survey (online, Telehealth, telephone, or text messaging). This Survey will include concomitant medication review and symptoms review.
- The Exit Contact Survey will include evaluation for SARS-CoV-2 infection and/or COVID-19 and associated testing and medical care.

- *If in DBS Sub-study, collect DBS samples for analysis of anti-SARS-CoV-2 antibodies (if possible).*

Clinical outcomes will be confirmed through the electronic health record, if possible.

The final swab will be collected by the courier or returned via the postal service.

9.1.5. *Participants who Develop COVID-19 During the Study*

Participants who develop symptoms concerning for COVID-19 will be instructed to contact their provider for clinical care and testing. Study results will be available to participants after study completion as they are not tested in real-time for clinical diagnosis.

Participants who develop SARS-CoV-2 infection may be sent a home pulse oximeter to measure the oxygen saturation to provide direct information for clinical assessment.

Participants with a clinical diagnosis of COVID-19 should continue on study therapy unless they are started on COVID-19 treatment outside this study. Other study procedures will continue, with early exit possible to document COVID-19 diagnosis.

9.2. *Index Cases*

9.2.1. *Baseline Evaluation: Day 1*

Participants will be assessed for study eligibility through a screening conducted through a web-based screening tool, Telehealth, telephone, or text messaging.

Day 1 evaluations are as follows:

- *Informed consent*
- *Collection of demographic information*
- *Check of inclusion and exclusion criteria*

Eligible participants will receive a swab kit either via courier or mail, which includes a Quick Start Instruction Card, a swab, a plastic tube for swab collection, and a return container with affixed Category B UN3373 label, as required by International Air Transport Association (IATA) guidelines [36].

The participant will do the following on Day 1:

- *Collect mid-nasal swab for PCR*
- *Complete Survey (online, Telehealth, telephone, or text messaging). This Survey will include assessment of risk for COVID-19 acquisition, engagement with testing and treatment, and symptom review.*

9.2.2. *Exit Contact (Day 28)*

The Exit Contact will be conducted through Telehealth, online, by telephone, or by text messaging.

Exit Contact evaluations are as follows:

- *Complete Exit Contact Survey (online, Telehealth, telephone, or text messaging). This Survey will include assessment of risk for COVID-19 acquisition, engagement with testing and treatment, and symptom review.*

Clinical outcomes will be confirmed through the electronic health record, if possible.

9.3. Participant Reimbursement

Participants will be reimbursed on Day 14 and Day 28. *Index cases enrolled in the index case sub-study will receive a reimbursement on Day 28.* No reimbursement will be provided to index cases for referral of their close contacts. No reimbursement will be provided for unscheduled Telehealth visits requested by the participants for support with study procedures.

10. Study Assessments and Procedures

- Study procedures and their timing are summarized in the SoA.
- Protocol waivers or exemptions are not allowed.
- Immediate safety concerns should be discussed with the sponsor immediately upon occurrence or awareness to determine if the participant should continue or discontinue study treatment.
- Adherence to the study design requirements, including those specified in the SoA, is essential and required for study conduct.
- All baseline evaluations must be completed and reviewed to confirm that potential participants meet all eligibility criteria. The Investigator will maintain a screening log to record details of all participants screened and to confirm eligibility or record reasons for screening failure, as applicable.
- Procedures conducted as part of the participant's routine clinical management and obtained before signing of the informed consent form may be utilized for screening or baseline purposes provided the procedures met the protocol-specified criteria and were performed within the time frame defined in the SoA.
- *Blood samples will only be collected as a part of a sub-study. The maximum amount of blood collected from each participant over the duration of the study, including any extra assessments that may be required, will not exceed 10 mL.*

10.1. Efficacy Assessments

10.1.1. Mid-nasal Swab

Participants will collect daily mid-nasal swabs for the initial 14 days and again at the Exit Contact for viral detection.

Index case participants in the index case sub-study will submit their baseline nasal swab for SARS-CoV-2 testing by PCR.

Participants will receive a swab kit either via courier or mail, which includes a Quick Start Instruction Card, swabs, plastic tubes for swab collection, and a return box with affixed Category B UN3373 label, as required by IATA guidelines [36].

Participants will collect and store their nasal swabs in a box for return.

The used swabs will be collected by the courier or returned via the postal service.

Swabs will be subjected to RNA amplification and tested for SARS-CoV-2, as applicable.

10.1.2. *Participant Survey*

Participants will be asked to complete Surveys (Daily Survey and Exit Contact Survey) that will include questions about symptoms from both the drug regimen and virus infection, review of concomitant medications, and other pertinent topics include information on any symptoms that may be associated with COVID-19.

10.2. *Adverse Events*

AE information will only be collected on close contact participants. For information regarding AEs in index case participants see [Section 10.2.7](#).

Participants will be asked to complete Surveys (Daily Survey and Exit Contact Survey) that include information on any symptoms that they are experiencing. In addition, AE review by a staff member (via telephone, Telehealth, or text messaging) will be performed.

All AEs must be recorded on electronic case report forms (eCRFs) if any of the following criteria have been met:

- All AEs meeting SAE definition
- All AEs judged by participant or clinician to be associated with study medication

10.2.1. *Serious Adverse Events*

An SAE is defined as any untoward medical occurrence that:

- Results in death
- Is life-threatening
- Requires inpatient hospitalization or prolongation of existing hospitalization
- Results in persistent or significant disability/incapacity
- Is an important medical event that may not be immediately life-threatening or result in death or hospitalization but may jeopardize the patient or may require intervention to prevent one of the other outcomes listed in the definition above

All AEs that are recorded will have their severity graded. To grade AEs, sites should refer to the DAIDS AE Grading Table, corrected Version 2.1, July 2017, which can be found on the DAIDS Regulatory Support Center website at [https://rsc.tech-res.com/docs/default-source/safety/division-of-aids-\(daids\)-table-for-grading-the-severity-of-adult-and-pediatric-adverse-events-corrected-v-2-1.pdf](https://rsc.tech-res.com/docs/default-source/safety/division-of-aids-(daids)-table-for-grading-the-severity-of-adult-and-pediatric-adverse-events-corrected-v-2-1.pdf).

10.2.2. AE and SAE Attribution to Study Medication

All AEs and SAEs should have attribution recorded as related or not related to study medication, in the judgment of the site Investigator.

10.2.3. AE and SAE Reporting

- SAEs will be reported within 48 hours to the Sponsor.
- Grade 3 and 4 AEs assessed as related to the study medication by the clinician will be reported to the Sponsor within 48 hours.
- Grade 1 and 2 AEs assessed as related to the study medication by the clinician will be reported to the Sponsor within 2 weeks of the participant's Exit Contact.

10.2.4. Reporting of Use During Pregnancy

- Medication exposure during pregnancy will be reported to the Sponsor within 2 weeks of *the participant's Exit Contact*.

10.2.5. Reporting of Misuse of Drug

- Misuse and abuse of medication outside the protocol will be reported to the Sponsor within 2 weeks of *the participant's Exit Contact*.

10.2.6. Treatment of Overdose

Overdose of HCQ should be managed according to the labeling information (see [Appendix 4](#)).

Ascorbic acid exhibits low toxicity; risks from overdose are expected to be minimal.

Overdose of study medication should be reported to the Sponsor within 48 hours.

10.2.7. AEs Among Index Case Participants

AEs among the index case participants in the index case sub-study will not be collected or reported as index cases are not receiving study medication or interventions.

10.3. Safety and AE Assessments

Safety will be assessed via participant Surveys, as shown in the SoA.

Participants will be asked to complete Surveys (Daily Survey and Exit Contact Survey) that include questions about their health, healthcare seeking, symptoms, illness within their household, contact, and mobility. Qualifying events will be recorded on the eCRF and reported as AEs, as described in [Section 10.2](#).

Social harms will be assessed throughout the study, reported using the Social Harms form, and reported to the Sponsor within 48 hours.

10.4. Dried Blood Spot Optional Sub-study

Up to 1800 participants will be enrolled in the DBS Sub-study. DBS will be requested, but not required, of all participants. For those study sites not wishing to participate in the DBS Sub-study, this will not be considered a protocol deviation.

Participants will receive instructions for DBS self-collection in writing, with telephone, Telehealth, and text messaging options as support. Once cards have been dried, they will be collected by the study courier and returned to the laboratory.

The aim of the DBS Sub-study is to evaluate HCQ drug concentrations as an adherence measure and the PK of HCQ. If serological assays for SARS-CoV-2 are available, DBS may be tested for SARS-CoV-2 antibodies.

Pharmacokinetics

The exposure-response relationship of HCQ in the PEP of participants exposed to SARS-CoV-2 has not been established. Population PK analyses can be used to further inform dose selection in other populations and support concentration-response investigations with efficacy and safety outcomes.

To accomplish this, sparse PK sampling techniques can be employed. This would involve collection of whole blood at 1 to 5 times after dosing has commenced. The time of collection post-dose can be random; however, no more than 1 sample per day should be collected.

Given the long half-life of HCQ, samples for several weeks after the last dose are also informative to the population PK model development.

The basic requirements for PK sampling are as follows:

- 1. Accurate record of time of the dose prior to the blood sampling (dd:mm:yy; hh:mm)*
- 2. Accurate recording of time of blood sampling (dd:mm:yy; hh:mm) for each blood sampling.*
- 3. Whole blood can be obtained by venipuncture or capillary blood by skin puncture using a lancet.*
- 4. Approximately 100 μ L of blood is then applied to filter paper as outlined in [Appendix 6](#).*

Anti-SARS-CoV-2 Antibody Testing

DBS sample for serology will be collected at Day 1 and Day 28 and tested for SARS-CoV-2 antibodies provided that an appropriate test is available.

10.5. Genetic Testing

10.5.1. Samples Used for Genetic Testing

Dried blood spot and mid-nasal swab samples collected in the study could be used potentially for genetic studies. During the consent process, participants can opt out of genetic testing.

10.5.2. Genetic Testing Procedures

Studies conducted on stored samples will investigate genes that may play a role in susceptibility to SARS-CoV-2 infection or other respiratory viruses and/or severity of COVID-19. The samples

will not be used to study genes related to diseases other than SARS-CoV-2 or other respiratory viruses.

10.5.3. Genetic Information That Will Be Obtained

Samples will be tested for the presence of genetic markers, which the investigators believe, on the basis of available medical literature, to possibly be rationally associated with susceptibility to SARS-CoV-2 infection and/or the severity of COVID-19. Genome-wide screening (such as “SNP screening”) is not planned.

10.6. Biohazard Containment

As the transmission of SARS-CoV-2 and other respiratory droplet pathogens can occur through contact with respiratory droplets and contaminated surfaces, precautions will be employed by all personnel in the handling of all specimens for this study, as currently recommended by the Centers for Disease Control and Prevention and the National Institutes of Health.

All dangerous goods and materials, including diagnostic specimens and infectious substances, must be transported using packaging mandated by Code of Federal Regulations 42 Part 72. Please refer to instructions detailed in the IATA Dangerous Goods Regulations.

11. Statistical Considerations

11.1. Sample Size Determination

Not all individuals exposed to COVID-19 will become infected, and early estimates place family members at a 3% to 15% risk of infection after likely exposure [32, 33]. The sample size required to show a 50% protective efficacy of PEP is entirely dependent on that attack rate. Sample size calculations used an estimated 6% attack rate.

A sample size will be chosen for each group (HCQ and ascorbic acid) to achieve 80% power with 0.05 two-sided Type 1 error for the endpoint of any laboratory-detected incident SARS-CoV-2, exclusion of participants with positive SARS-CoV-2 at baseline, an attack rate of 6%, 50% efficacy of HCQ in reducing SARS-CoV-2 incidence, and randomizing the first household member enrolled and subsequent household members to the same intervention. With these assumptions, a cohort of 1498 households (749 in the control and 749 in the intervention for each cohort) will provide at least 80% power to detect a decrease in SARS-CoV-2 incidence from 6% to 3%. As household size increases, power will increase.

Household members will be randomized as a unit but analyzed as individuals.

The table below estimates power assuming that households are randomized until either 1498 households are randomized or 1498 individuals are randomized. Each row shows the distribution of the numbers of individuals within a household who are randomized. Individual risk is assumed to be independent. Power may be lower depending on correlation in risk within and between households (Table 1).

Table 1 Power to Detect a Decrease from 6% to 3% Under Hypothetical Distributions of Number of Household Contacts

Number in Household	Distribution of Number Randomized Within Household					Number of Households is the Target			Number of Participants is the Target		
	1	2	3	4	5	N _{HH}	N _p	Power	N _{HH}	N _p	Power
A	0.8	0.1	0.06	0.03	0.01	1498	2022	89%	1108	1498	78%
B	0.75	0.15	0.06	0.03	0.01	1498	2097	90%	1070	1498	78%
C	0.25	0.35	0.16	0.13	0.11	1498	3745	99%	600	1498	76%

N_{HH}: number of households; N_p: number of participants.

These power calculations indicate that final power will depend heavily on the population enrolled. To mitigate the potential loss in power from lack of information about cluster size, the final target sample size will be estimated midway through the study based on the observed distribution of the number of household contacts. The procedure for redetermining sample size will be described in an Interim Monitoring Plan approved by the DSMB.

11.2. Populations for Analyses

For analysis purposes, the following populations are defined:

Population	Description
Intention to Treat	All enrolled participants who are contacts
Modified Intention to Treat (MITT)	Contacts who are SARS-CoV-2 negative by PCR at the baseline visit and whose corresponding index case is SARS-CoV-2 positive by report or PCR
PK evaluable	Participants from the DBS Sub-study with at least 1 interpretable PK sample

DBS: dried blood spot; PK: pharmacokinetic; PCR: polymerase chain reaction; SARS-CoV-2: severe acute respiratory syndrome coronavirus 2.

Note: All PCR negative household contacts will be included in the MITT analyses.

11.3. Statistical Analyses

The Statistical Analysis Plan will be developed and finalized before database lock and will describe the participant populations to be included in the analyses, and procedures for accounting for missing, unused, and spurious data. This section is a summary of the planned statistical analyses of the primary and secondary endpoints (these are listed in [Section 4](#)).

11.3.1. Efficacy Analyses

Demographic characteristics (age, sex, race) of each study group will be tabulated.

The mean age (plus range and standard deviation) by sex of the enrolled participants, as a whole and per group, will be calculated.

The primary analysis will be performed using the modified Intention-to-Treat population. If the participant is not SARS-CoV-2 positive by laboratory test, their infection time will be censored at the last negative swab test date at or before the Day 14 swab. A logistic model stratified by site and accounting for within-household correlation will be used to assess the efficacy of the HCQ group compared to control. To aid understanding of the results from the logistic model, cumulative incidence Kaplan-Meier curves of time to infection will be presented by site and treatment arm.

Subgroup Analyses

All subgroup analyses will be pre-specified in the Statistical Analysis Plan. Any further subgroups will be considered *ad hoc*.

Missing Data

Due to the design of the study and retention activities, we expect to be able to categorize all infections as either incident or prevalent at baseline. However, in the unlikely event of a missing test result, the missing data will be imputed.

Additional analyses will be described in the Statistical Analysis Plan finalized before database lock.

11.3.2. Safety Analyses

All safety analyses will be performed on the Intention-to-Treat population. AEs and social harms will be compared by study group.

11.3.3. Pharmacokinetic Analysis

Sparse PK from DBS will be analyzed using standard population PK analysis methodologies using standard software such as NONMEM® V7.4 or Phoenix NLME V8.2.

11.3.4. Exploratory Exposure-Response Analyses

PK-evaluable participants will have post-hoc individual concentration profiles and exposure estimates determined for exploratory exposure-response analyses against primary and secondary efficacy and safety endpoints. Exploratory PK/pharmacodynamic analyses will be performed as the data allow.

11.3.5. Exploratory Transmission Analyses

The index case sub-study will assess the risk of SARS-CoV-2 transmission and the association with the semi-quantitative PCR results. Also, the risk of transmission between close contacts will be assessed by determining whether the viruses are a genetic match among household members through SARS-CoV-2 sequencing.

11.3.6. *Combined Study Analysis*

This protocol is being published as a model protocol for other institutions to consider as they undertake studying PEP of SARS-CoV-2 infection. It is hoped that individual patient data from similar studies can be pooled into a combined study analysis. De-identified data from the present study will be made available for these purposes in accordance with the funder's open access policy (<https://www.gatesfoundation.org/how-we-work/general-information/open-access-policy>).

12. References

4. WHO News Release. Statement on the second meeting of the International Health Regulations (2005) Emergency Committee regarding the outbreak of novel coronavirus (2019-nCoV). 2020 Jan 30.
5. White House Press Release. <https://www.whitehouse.gov/presidential-actions/proclamation-declaring-national-emergency-concerning-novel-coronavirus-disease-covid-19-outbreak>. 2020 Mar 13.

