3.2.6. Rationale for Enrolling the Index Case for the Index Case Sub-study

The quantity of the virus shed by an individual frequently predicts transmissibility, and thus may relate to the likelihood of SARS-CoV-2 transmission. Index cases will be enrolled, and a nasal swab collected for SARS-CoV-2 testing to ascertain whether the index case was shedding virus and the level of viral shedding. The genotype of the virus shed will be investigated in a subset of participants. Evaluation of the paired samples (index case and contact) will provide evidence on whether the level of shedding is associated with SARS-CoV-2 transmission and whether subsequent infections among contacts were acquired within households.

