6.1. Close Contact Participants

6.1.1. Inclusion Criteria

Participants are eligible to be included in the study only if all of the following criteria apply:

1. Men or women 18 to 80 years of age inclusive, at the time of signing the informed consent
2. Willing and able to provide informed consent
3. Had a close contact of a person (index) with known PCR-confirmed SARS-CoV-2 infection or index who is currently being assessed for COVID-19

Close contact is defined as:

- a. Household contact (i.e., residing with the index case in the 14 days prior to index diagnosis or prolonged exposure within a residence/vehicle/enclosed space without maintaining social distance)
 - b. Medical staff, first responders, or other care persons who cared for the index case without personal protection (mask and gloves)
4. Less than 4 days since last exposure (close contact with a person with SARS-CoV-2 infection) to the index case
 5. Access to device and internet for Telehealth visits
 6. Not planning to take HCQ in addition to the study medication

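### In section 11.3.5 a genetic match within a household cannot show transmission between contacts, because contacts infected separately by the same index case are expected to match too

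*Protocol*

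**What the plan says.** Protocol section 11.3.5 has two sentences on transmission. The first concerns the index case: "The index case sub-study will assess the risk of SARS-CoV-2 transmission and the association with the semi-quantitative PCR results". The second adds that "the risk of transmission between close contacts will be assessed by determining whether the viruses are a genetic match among household members", by sequencing. The section does not define a match or set a threshold. It does not use the order of infection and gives no comparison rate.

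Section 3.2.6, the rationale for enrolling index cases, claims less. Its pairs are an index case with a contact, and the question beyond shedding level is "whether subsequent infections among contacts were acquired within households". It also limits the material: "The genotype of the virus shed will be investigated in a subset of participants".

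Section 6.1.1 defines a household contact by the link to the index case, either "residing with the index case in the 14 days prior to index diagnosis" or prolonged exposure in an enclosed space.

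The SAP adds nothing on this analysis. Section 2.2 confines it to the primary and secondary objectives. Section 3.1 defines a Household Cohort, but no analysis is attached to it.

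**The concern.** Sequence agreement is informative about who infected whom only if the competing routes predict different agreement. Here they hardly do. If the index case infects two contacts separately, both viruses descend from one source one step back. If one contact infects the other, the viruses are also one step apart. Matching is expected either way, and it is the only input named for the contact-to-contact question.

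At stake is what the trial can say about spread among contacts. Section 5.1 gives the extent of transmission within household contacts as a purpose of the index case sub-study, and section 11.3.6 offers the protocol as a model for other institutions. A figure for contact-to-contact risk built on matching alone could not be interpreted, and other sites could copy the method.

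A smaller gap affects the narrower household question as well. Without a background match rate from different households, a common local strain would be counted as acquisition within the household.

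**Working it through.** The documents give no figure for this analysis, so there is nothing to reproduce. The checks below are illustrations with stated assumptions.

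**1. How far a match separates the routes.** Assume the number of sequence changes per transmission link is Poisson with mean μ, and take μ from 0.1 to 0.5. Both the model and the range are assumptions. Two contacts infected separately by the index are two links apart, so they differ by Poisson(2μ). A direct pair differs by Poisson(μ).

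| Match rule | μ | Both from index | Contact to contact | Ratio |
|---|---|---|---|---|
| ≤2 differences | 0.1 | 0.999 | 1.000 | 1.00 |
| ≤2 differences | 0.3 | 0.977 | 0.996 | 1.02 |
| ≤2 differences | 0.5 | 0.920 | 0.986 | 1.07 |
| identical | 0.1 | 0.82 | 0.90 | 1.11 |
| identical | 0.3 | 0.55 | 0.74 | 1.35 |
| identical | 0.5 | 0.37 | 0.61 | 1.65 |

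For identity the entries are exp(−2μ) and exp(−μ). For ≤2 differences, an example at μ = 0.5 is exp(−1) × (1 + 1 + 0.5) = 0.920. The last column is the likelihood ratio that a match supplies in favour of direct spread: 1.00 to 1.07 under the looser rule and 1.11 to 1.65 under the strict one. Neither separates the routes well. Under strict identity, exp(−2μ) exceeds 0.5 only for μ below ln 2 / 2 ≈ 0.35.

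**2. Infections from outside the household.** Suppose there is no contact-to-contact spread, a share m of contact infections comes from the index, those viruses match, and outside strains never match. A pair of infected contacts then matches with probability m². This is 0.64 at m = 0.8 and 0.90 at m = 0.95, still far from zero.

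**3. What share of matched pairs is direct.** Take a two-contact household. The index infects each contact with probability p, and an infected contact infects the other with probability q. If every such pair matches, the direct share is 2p(1−p)q / [2p(1−p)q + p²]. With p = 0.06 from Protocol section 11.1 ("Sample size calculations used an estimated 6% attack rate"), p² = 0.0036:

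| Assumed q | 2p(1−p)q | Direct share |
|---|---|---|
| 0 | 0 | 0% |
| 0.03 | 0.00338 | 48% |
| 0.06 | 0.00677 | 65% |
| 0.12 | 0.01354 | 79% |

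The match probability given two infected contacts is the same in every row, so the share that matches carries no information about q.

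**4. How many households are involved.** Inputs are Table 1 of Protocol section 11.1 (household-size fractions f_k, with household counts for the 1498-participant target) and attack rates: the protocol range ("early estimates place family members at a 3% to 15% risk of infection after likely exposure"), its 6%, and the 10% for the placebo arm in SAP section 2.4. With q = 0 and independent risks, the expected number of households with at least two infected contacts is N_HH × Σ f_k × P(Bin(k, p) ≥ 2). For row A at 6%, the probabilities for k = 2 to 5 are 0.0036, 0.0104, 0.0199 and 0.0319. The weighted sum is 0.00190, and 1108 × 0.00190 = 2.1.

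| Table 1 row (households) | 3% | 6% | 10% | 15% |
|---|---|---|---|---|
| A (1108) | 0.5 | 2.1 | 5.6 | 12.0 |
| B (1070) | 0.6 | 2.2 | 6.0 | 12.8 |
| C (600) | 1.4 | 5.4 | 14.2 | 30.0 |

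These counts are before any restriction to the genotyped subset. They leave out contacts already positive at baseline, who stay in the study under section 8.1 and would add multi-case households.

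**5. What other data could separate the routes.** Adding the index sequence does not settle it: under either route all three viruses are expected to match. Order of infection is available from the daily swabs (section 10.1.1). Exposure to the index case is scheduled only at Day 0 (sections 2 and 9.1.1). The later surveys ask in general terms about household illness and contact (section 10.3), with no dated exposure to the index specified.

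**The case against.** The strongest reply is that the protocol says the risk will be assessed by matching. It does not say that a matched pair will be classified as contact-to-contact transmission, and it gives no estimator. A reader might infer that most multi-case households will be reported as contact-to-contact spread and the risk badly overestimated. The documents do not support that: with no decision rule and no estimator, no bias can be computed. What stands is that no other input is named, so nothing in the plan limits the conclusion.

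Second, section 3.2.6 and the exploratory objective in section 4 concern index-to-contact transmission, and no listed objective concerns spread between contacts. The phrase in 11.3.5 may be loose wording for spread within the household, a question on which matching does bear. This is possible. However, the protocol treats close contacts and index cases as separate populations (sections 6.1 and 6.2), and 11.3.5 has already dealt with the index case in its own sentence. On either reading the sentence needs to be brought into line with 3.2.6.

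Third, the analysis is exploratory, and no primary, secondary, safety or monitoring result uses it. That stands in full and limits how much weight the point deserves.

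**Conclusion.** The point holds as a limit on inference. Matching among household members can argue against direct spread when it fails, but when it succeeds it cannot distinguish spread between contacts from separate infection by the shared index case. The logic needs only a common index case per household and closely related virus along either route; it does not depend on the Poisson model.

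The size is uncertain. The mutation rate and match threshold are assumptions. A reader might infer from the ≤2-difference figures that matching would occur in most separately infected pairs under any definition; under strict identity it falls below half once μ exceeds about 0.35. The household counts assume independent risks, one index case per household and the same attack rate in both arms. They suggest few informative households, particularly at 3% to 6%, and fewer after restriction to the genotyped subset. The effect is confined to this exploratory analysis.

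**What to change.** Amend section 11.3.5, or give the analysis its own plan, along these lines:

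- Define a match, and take it only as evidence of a shared household source, that is, acquisition within the household as in section 3.2.6.
- Report index-to-contact and contact-to-contact matches separately. Set both against the match rate between pairs from different households at the same site and in the same calendar period.
- For matched contact pairs, describe the order of and gap between first-positive daily swabs. Report the pair as indeterminate for contact-to-contact spread unless the available timing and exposure data make infection by the index unlikely.

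The cost is wording and a modest amount of extra analysis. The comparison uses sequences already planned, and no new samples are needed. The drawback is that most matched contact pairs will be indeterminate, because index-exposure information is scheduled only at Day 0 and contacts who live with the index may remain exposed.
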